## **2.4 Treatments (study treatment, rescue medication, concomitant therapies, compliance)**

### **2.4.1 Study treatment / compliance**

The total number of subjects who received an injection of study treatment will be presented.

### **2.4.2 Prior, concomitant and post therapies**

Medications will be coded according to the Anatomical Therapeutic Chemical (ATC) classification system.

Non-drug therapies and procedures will be coded using MedDRA Version 21.1.

Prior and concomitant medications and non-drug therapies and procedures will be listed.

## **2.5 Analysis of the primary objective**

### **2.5.1 Primary endpoint**

The incidence of ocular and non-ocular AEs are the primary endpoints. The primary endpoints will be analyzed for the FAS.

## **2.5.2 Statistical hypothesis, model, and method of analysis**

No formal hypothesis testing will be performed in this study.

See [Section 2.8.1](#) for details of the analyses to be performed for AEs.

## **2.5.3 Handling of missing values/censoring/discontinuations**

This is a single dose, open-label study with 2 scheduled visits over the period of 1 week. Therefore, missing data will not be imputed.

## **2.5.4 Supportive analyses**

Not applicable.

## **2.6 Analysis of the key secondary objective**

No key secondary objectives are defined for this study.

## **2.7 Analysis of secondary efficacy objective(s)**

No secondary objectives are defined for this study.

## **2.8 Safety analyses**

All safety analyses will be performed for the FAS.

### **2.8.1 Adverse events**

AEs will be coded using MedDRA Version 21.1.

All AEs will be listed.

Summaries will include all treatment emergent AEs which are defined as AEs which start on or after the date of the injection of study treatment up until the patient discontinues or completes the study.

Analyses will be performed for ocular AEs for the study eye only and non-ocular AEs. Ocular and non-ocular AEs will be presented separately. Ocular AEs for the fellow eye will be listed only.

The number and percentage of subjects who reported treatment emergent AEs will be summarized by primary SOC and PT for:

- all AEs
- all AEs by maximum severity
- all AEs by investigator causality assessment (relationship to study treatment and/or study treatment administration procedure)
- AEs leading to study discontinuation
- all serious adverse events (SAE)

If a subject reports more than one AE with the same PT, the AE will be counted only once for that PT. If a subject reports more than one AE within the same primary SOC, the subject will be counted only once for that SOC.

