Information about common side effects already known about the investigational drug can be found in the Investigator's Brochure (IB). This information will be included in the subject informed consent and should be discussed with the subject during the study as needed. Any new information regarding the safety profile of the investigational drug that is identified between IB updates will be communicated as appropriate, for example, via an investigator notification (IN) or an aggregate safety finding. New information might require an update to the informed consent and then must be discussed with the subject.

Women of child bearing potential must be informed that taking the study treatment may involve unknown risks to the fetus if pregnancy were to occur during the study and agree that in order to participate in the study they must adhere to the contraception requirements.

A copy of the approved version of all consent forms must be provided to Novartis after IRB/IEC approval.

8 Visit schedule and assessments

The Assessment Schedule ([Table 8-1](#)) lists all of the assessments when they are performed. All data obtained from these assessments must be supported in the subject's source document.

Subjects should be seen for all visits/assessments as outlined in the Assessment Schedule ([Table 8-1](#)) or as close to the designated day/time as possible. Missed or rescheduled visits should not lead to automatic discontinuation. Subjects who prematurely discontinue the study for any reason should be scheduled for a visit as soon as possible, at which time all of the assessment of the final visit will be performed. At this final visit, the adverse event and concomitant medications should be recorded on the eCRF.

Table 8-1 Assessment Schedule

Period	Open Label Treatment	Post-Treatment Follow-Up	Follow up
Visit Name	Baseline	End of Study	Follow up
Days	1	8	31
Informed consent	X		
Inclusion / Exclusion criteria	X		
Demography	X		
Medical history/current medical conditions	X		
Concomitant medications	X	X	
Intraocular Pressure (IOP)	X	X	
Vital Signs	X	X	
Pregnancy Test	S		
Study drug administration	X		
Observation of PFS injection	S		
Adverse Events	X	X	S
Ocular Assessments (slitlamp, ophthalmoscopy)	S	S	

^X Assessment to be recorded in the clinical database or received electronically from a vendor

^S Assessment to be recorded in the source documentation only

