10.1 Definition of adverse events and reporting requirements

10.1.1 Adverse events

An adverse event (AE) is any untoward medical occurrence (eg, any unfavorable and unintended sign (including abnormal laboratory findings), symptom or disease) in a subject or clinical investigation subject after providing written informed consent for participation in the study. Therefore, an AE may or may not be temporally or causally associated with the use of a medicinal (investigational) product.

The investigator has the responsibility for managing the safety of individual subject and identifying adverse events.

Novartis qualified medical personnel will be readily available to advise on trial related medical questions or problems.

The occurrence of adverse events must be sought by non-directive questioning of the subject at each visit during the study. Adverse events also may be detected when they are volunteered by the subject during or between visits or through physical examination findings, laboratory test findings, or other assessments.

Adverse events must be recorded in the Adverse Events CRF under the signs, symptoms or diagnosis associated with them, accompanied by the following information (as far as possible) (if the event is serious refer to [Section 10.1.2](#)):

1. The severity grade includes the following:
 - mild: usually transient in nature and generally not interfering with normal activities
 - moderate: sufficiently discomforting to interfere with normal activities
 - severe: prevents normal activities
2. its relationship to the study treatment. If the event is due to lack of efficacy or progression of underlying illness (ie progression of the study indication) the assessment of causality will usually be 'Not suspected'. The rationale for this guidance is that the symptoms of a lack of efficacy or progression of underlying illness are not caused by the trial drug, they happen in spite of its administration and/or both lack of efficacy and progression of underlying disease can only be evaluated meaningfully by an analysis of cohorts, not on a single subject.
3. its duration (start and end dates) or if the event is ongoing, an outcome of not recovered/not resolved must be reported.
4. whether it constitutes a SAE (see [Section 10.1.2](#) for definition of SAE) and which seriousness criteria have been met.
5. action taken regarding with study treatment.

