12.4.2 Statistical model, hypothesis, and method of analysis

No formal hypothesis tests will be performed in this study. All safety analyses will be performed using the FAS.

Adverse events

The number (and percentage) of subjects with treatment-emergent adverse events (events started after the single dose of study treatment or events present prior to start of study treatment but which increased in severity based on preferred term) will be summarized in the following ways:

- by treatment, primary system organ class and preferred term
- by treatment, primary system organ class, preferred term and maximum severity
- by treatment, Standardized MedDRA Query (SMQ) and preferred term

Separate summaries will be provided for study treatment related adverse events, death, serious adverse events, other significant adverse events leading to discontinuation of the study. Separate presentations will be provided related to ocular events in the study eye and fellow eye and systemic events. Additional summaries will be provided by severity and causality (separately assessed for the injection procedure and the drug). Subject listings of all adverse events will be provided. Deaths and other serious or clinically significant non-fatal adverse events will be listed separately.

A subject with multiple adverse events within a primary system organ class is only counted once towards the total of the primary system organ class.

Ophthalmic examinations

Pre-injection and post-injection IOP measurements will be listed.

Vital signs

All vital signs data will be listed by subject and, if ranges are available, abnormalities will be flagged with thresholds representing clinical relevant abnormality.

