**Document History – Changes compared to previous final version of SAP**

Date	Time point	Reason for update	Outcome of update	Section and title impacted (Current)
9 Aug 2019	Prior to DBL	Data is coded with MedDRA V21.1	References to “most recent version at the time of DBL” changed to reflect Version 21.1 is used	S2.3.2 Subject demographics and baseline characteristics S2.4.2 Prior, concomitant and post therapies S2.8.1 Adverse events
9 Aug 2019	Prior to DBL	Sites have entered events prior to IFC on the eCRF	Text updated to reflect prior non-drug therapies and procedures are included in the listing	S2.4.2 Prior, concomitant and post therapies
9 Aug 2019	Prior to DBL	Criteria changed from increase $\geq$ 20 mmHg from pre-injection IOP to post-injection IOP within a visit to an increase $\geq$ 10 mmHg	Text stating the criteria is updated	Section 2.8.3.1 Intraocular pressure (IOP) (mmHg)
9 Aug 2019	Prior to DBL	Imputation of partial dates for medications is not required for any analyses	Section 5.1.2 removed	S5.1.2 Concomitant medication date imputation

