### **2.1.1.1 Study day**

Study day is defined as the number of days since the date of the injection of study treatment. The date of the injection of study treatment will be defined as Day 1 and the day before the injection of study treatment will be defined as Day -1.

Therefore, for a particular date, study day will be calculated as follows:

- For dates on or after the date of the injection of study treatment,  
Study day = Visit/Assessment date – date of injection of study treatment + 1
- For dates prior to the date of the injection of study treatment,  
Study day = Visit/Assessment date – date of injection of study treatment

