## 4 Change to protocol specified analyses

Protocol section 12.2 states that relevant medical histories and current medical conditions at baseline will be summarized. Given the small sample size this data will be listed only.

Protocol section 12.3 states that descriptive statistics for exposure to study treatment and the cumulative number of injections will be presented. As subjects are only scheduled to receive a single injection of study treatment the total number of patients who received an injection will be presented.

Protocol section 12.3 states that concomitant medications and significant non-drug therapies prior to and after the start of the study treatment will be summarized. Given the small sample size this data will be listed only.

Protocol section 12.4.2 states that treatment emergent AEs will be summarized by SMQ and PT. This summary will not be produced, treatment emergent AEs will be presented by SOC and PT only.

Protocol section 12.4.2 states that AE presentations will be presented for the fellow eye. Adverse events for the fellow eye will be listed only.

Protocol section 12.4.2 states that pre-injection and post-injection IOP measurements will be listed. Instead, IOP measurements will only be listed for subjects who have at least IOP measurement meeting the criteria defined in SAP [Section 2.8.3.1](#).

Protocol section 12.4.2 states that all vital signs data will be listed. Instead, vital signs measurements will only be listed for subjects who have at least one vital signs measurement meeting the criteria defined in SAP [Section 2.8.3.2](#).

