  - c. Else if the AE month is equal to the treatment start date month or greater than the treatment start date month, the imputed AE start date is set to the later of (month start point (01MONYYYY), AE start reference date + 1 day).

If complete (imputed) AE end date is available and the imputed AE start date is greater than the (imputed) AE end date, then imputed AE start date should be set to the (imputed) AE end date.

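### SAP 2.8.1 defines treatment-emergent AEs by start date alone and drops the protocol's worsening rule without declaring it in SAP Section 4

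*SAP*

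**What the plan says.** The sole objective is safety, and the sole endpoint is the incidence of ocular and non-ocular AEs (Protocol Table 2-1; SAP Table 1-1 and 2.5.1).

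Protocol 12.4.2 gives two routes by which an AE becomes treatment-emergent. It either began after the single dose, or belongs to "events present prior to start of study treatment but which increased in severity based on preferred term".

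SAP 2.8.1 gives one route. Summaries cover "all treatment emergent AEs which are defined as AEs which start on or after the date of the injection of study treatment", until the subject discontinues or completes. All AEs are listed. Study-eye ocular AEs and non-ocular AEs are summarised separately, and fellow-eye AEs are listed only.

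SAP Section 4 sets out where the SAP departs from the protocol. One entry, on the dropped summary by standardised MedDRA query, reads "This summary will not be produced, treatment emergent AEs will be presented by SOC and PT only". No entry concerns which AEs count as treatment-emergent.

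**The concern.** The rule deciding which AEs are treatment-emergent fixes the numerator of the only endpoint. Every AE summary in SAP 2.8.1 depends on it. The protocol states one rule and the SAP applies a narrower one. A reader who uses Section 4 to learn what changed would conclude that the protocol's rule still applies.

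The events at stake are AEs that are already open before the injection date, become more severe after the injection, and keep their original start date. They would appear in the listing and in no summary table. In a safety study, worsening after an injection is something the summaries ought to show.

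**Working it through.** No figure in the plan needs reproducing: there is no power calculation and no hypothesis test. The check sets the texts side by side and then asks when the difference can matter.

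**1. Is the second route restored elsewhere in the SAP?** No. SAP 2.8.1 is the only definition. The SAP appendix covers date imputation, the absence of statistical models and the analysis set.

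**2. Is the change declared?** SAP Section 4 has seven entries: one against Protocol 12.2 (medical history), two against 12.3 (exposure; concomitant therapies) and four against 12.4.2 (the standardised-query summary, fellow-eye AEs, the IOP listing, the vital signs listing). 1 + 2 + 4 = 7, and none concerns the treatment-emergent definition.

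**3. Which events can be affected?** Under Protocol 10.1.1 an AE is an occurrence "in a subject or clinical investigation subject after providing written informed consent for participation in the study", so no AE starts before consent. Under SAP 2.1.1.1 the injection date is Day 1 and "the day before the injection of study treatment will be defined as Day -1". Let D be the injection date.

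- *Consent and injection both on D*, as in Protocol Table 8-1. The earliest AE start is D, and study day = D − D + 1 = 1. This meets the SAP's start-date rule, so no AE is lost.
- *Consent on D − 1.* An AE starting that day has study day = (D − 1) − D = −1. It fails the SAP rule even if it worsens after injection. Protocol 12.4.2 would count it.
- *Start day missing, month equal to the injection month, AE not ended before injection.* The reference date is D. SAP 5.1.1.2 rule 4c ("Else if the AE month is equal to the treatment start date month or greater than the treatment start date month") sets the start to the later of the first of the month and D + 1. That is D + 1, or study day 2, so the AE is counted.
- *Start day missing, month or year earlier than the injection's.* Rules 2b and 4b impute the middle of that earlier month. The AE is treated as starting before injection and is not counted.

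What remains is an AE with a complete start date before injection, or a partial date in an earlier month or year.

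**4. Can consent precede injection?** Protocol Section 3 and SAP 1.1 say that screening and baseline may fall on the same day, and the protocol summary says that they may be combined. That permits one visit without requiring it. The imputation matrix in SAP 5.1.1.2 has cells for AEs starting before treatment. Against this, Protocol 8.1.1 plans no separate screening period and has eligibility assessed at Baseline.

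**5. Size per affected subject.** The planned number is about 30. A subject who has no other treatment-emergent AE in the same group (study-eye ocular or non-ocular) lowers that group's incidence by 1/30 = 3.3 percentage points. If about 30 turns out to be 35 or 25 (assumed values), the figure is 1/35 = 2.9 or 1/25 = 4.0 points. Fellow-eye events move no summary.

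**6. Direction.** Leaving out the worsening route can, taken alone, only lower incidence. The start-date rule also works the other way: it counts AEs that began on Day 1 before the injection, which the protocol would count only if they worsened.

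**The case against.** The strongest reply is that the omission has no effect under the trial as scheduled. Table 8-1 has a single pre-injection column, Day 1, which holds both consent and injection, and Protocol 8.1.1 plans no separate screening period. An event is lost only if consent comes at least a day earlier, an AE starts in that gap, it worsens after injection, and the worsening stays under the original start date. This stands, and it is why the point is minor.

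A second reply is that worsening of baseline conditions is largely handled already. Conditions present at consent go to medical history (Protocol 10.1.1). The serious-AE definition in Protocol 10.1.2 treats the worsening of something pre-existing as an adverse event. On that reading, a baseline condition that worsens after injection becomes a new AE with a post-injection start, and the SAP counts it. A reader might infer that the SAP loses worsened baseline disease in general; the documents do not support that. The reply does not reach an AE already open between consent and injection. Protocol 10.1.1 follows changes in severity within an existing AE, and neither document tells sites to open a new record when one worsens.

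A third reply is that all AEs are listed and nothing is tested. Both are true, but a listing does not correct an incidence table, and neither fact reconciles the two definitions.

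**Conclusion.** The mismatch is clear on the text: the protocol has two routes to treatment-emergent status, the SAP keeps one, and Section 4 is silent. This is a changed counting rule for the only endpoint, not a missing detail. It is minor.

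The expected effect is at or near zero where consent and injection share a day. Elsewhere it is 3.3 percentage points per affected subject at n = 30, provided that the subject has no other treatment-emergent AE in the same group. The number of affected subjects is unknown, so the figure is illustrative and not an estimate of bias.

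A reader might infer that reported incidence will be biased downwards. The documents do not support that. The downward direction belongs to the missing route alone, and the Day 1 rule can push the count up. On a same-day schedule, the two onset rules can differ only upwards. Confidence is high on the textual mismatch; it does not extend to any effect on reported incidence.

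**What to change.** Add to the definition in SAP 2.8.1 a second category: AEs present before the injection whose severity increased after it, judged by preferred term. This brings the SAP into line with Protocol 12.4.2.

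First confirm that the database can support it. Protocol 10.1.1 asks for a severity grade for each AE and for changes in severity to be assessed, but does not say that dated changes are entered. If they are not recorded, declare the narrower definition in SAP Section 4 and give the reason.

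The first option costs one clause and a small programming change, and incidence may be slightly less favourable if a worsened event is then counted. The second costs one entry in Section 4 and needs no new data.

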Period	A minor subdivision of the study timeline; divides phases into smaller functional segments such as screening, baseline, titration, washout, etc.
Personal Data	Subject information collected by the Investigator that is transferred to Novartis for the purpose of the clinical trial. This data includes subject identifier information, study information and biological samples.
Screen Failure	A subject who is screened but is not treated or randomized
Source Data	Source data refers to the initial record, document, or primary location from where data comes. The data source can be a database, a dataset, a spreadsheet or even hard-coded data, such as paper or eSource.
Study completion	Point/time at which the subject came in for a final evaluation visit or when study drug was discontinued whichever is later.
Study treatment	Any drug (or combination of drugs) administered to the study participants as part of the required study procedures; includes investigational drug(s), control(s) or non-investigational medicinal product(s)
Subject	An individual who has consented to participate in this study. The term Subject may be used to describe either a healthy volunteer or a patient.
Subject number	A unique number assigned to each subject upon signing the informed consent. This number is the definitive, unique identifier for the subject and should be used to identify the subject throughout the study for all data collected, sample labels, etc.
Variable	Information used in the data analysis; derived directly or indirectly from data collected using specified assessments at specified timepoints.

Withdrawal of consent (WoC)	Withdrawal of consent from the study is defined as when a subject does not want to participate in the study any longer, and does not want any further visits or assessments, and does not want any further study related contact, and does not allow analysis of already obtained biologic material
-----------------------------	-----------------------------------------------------------------------------------------------------------------------------------------------------------------------------------------------------------------------------------------------------------------------------------------------------

Amendment 1

Amendment rationale

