4.2 Rationale for dose/regimen and duration of treatment

Each subject who enters the study will be given one injection of brolucizumab 6 mg in PFS. Previously performed studies in this indication suggest that brolucizumab 6 mg dose is effective and safe. One injection will be given in order to support the observation of the successful use of the device (PFS). After this injection, the follow up visit at Day 8 will be performed and there will be a safety follow-up phone call at Day 31. Subjects will be considered to have completed the study after the evaluations at Visit 2. The investigator will recommend the appropriate follow-up medical care, as needed and according to the clinical practice, for all subjects who completed the study.

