6.1.3 Treatment duration

One injection of brolucizumab 6 mg PFS per subject will be administered at Baseline, with one End of Study follow up visit after 7 days (\pm 2 days).

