8.1.1 Information to be collected on screening failures

There is no separate screening period planned for this study. Subject's Eligibility will be assessed at the Baseline Visit.

Subjects who sign an informed consent but do not receive the IVT injection will be considered a screen failure. The demographic information, informed consent, and Inclusion/Exclusion data must be completed in the eCRF and also be kept in the source documents for screen failure subjects. No further data will be entered into the clinical database for subjects who are screen failures, except if subject experienced a serious adverse event (see SAE section for reporting details).

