10.1.3 SAE reporting

To ensure subject safety, every SAE, regardless of causality, occurring after the subject has provided informed consent and until 30 days following the last administration of study treatment must be reported to Novartis safety within 24 hours of learning of its occurrence. Detailed instructions regarding the submission process and requirements are to be found in the investigator folder provided to each site.

All follow-up information for the SAE including information on complications, progression of the initial SAE and recurrent episodes must be reported as follow-up to the original episode within 24 hours of the investigator receiving the follow-up information. An SAE occurring at a different time interval or otherwise considered completely unrelated to a previously reported one must be reported separately as a new event.

If the SAE is not previously documented in the Investigator's Brochure or Package Insert (new occurrence) and is thought to be related to the study treatment, a chief medical officer & patient safety (CMO & PS) Department associate may urgently require further information from the investigator for health authority reporting. Novartis may need to issue an Investigator Notification (IN) to inform all investigators involved in any study with the same study treatment that this SAE has been reported.

Suspected Unexpected Serious Adverse Reactions (SUSARs) will be collected and reported to the competent authorities and relevant ethics committees in accordance with European Union (EU) Guidance 2011/C 172/01 or as per national regulatory requirements in participating countries.

Safety events occurring during the study will be reported as AEs in the eCRF. Device malfunction observations are to be reported to the respective Novartis Country Organization Quality Assurance.

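### SAEs starting between Visit 2 and Day 31 are reportable but cannot be counted in the SAE tables: the SAP window closes at Visit 2, and the protocol's schedule states no eCRF route after it

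*SAP*

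**What the plan says.** SAP 2.8.1 defines the treatment-emergent AEs that enter the summaries as "AEs which start on or after the date of the injection of study treatment up until the patient discontinues or completes the study". The SAE summary is one of the tables under that rule. SAP 2.8.1.1 (ClinicalTrials.gov tables) and SAP 2.8.2 (deaths) use the same term; 2.8.2 does not define a treatment-emergent death. SAP 2.1.1.4 makes the end of study a subject-level date.

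The protocol fixes that date. Section 4.2: "Subjects will be considered to have completed the study after the evaluations at Visit 2". The glossary entry for study completion agrees: "Point/time at which the subject came in for a final evaluation visit or when study drug was discontinued whichever is later". With a single injection, the visit is the later of the two. Section 6.1.3 provides for one injection at Baseline, "with one End of Study follow up visit after 7 days", with a window of 2 days either side.

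SAE reporting runs longer. Protocol 10.1.3 requires that every SAE from consent "until 30 days following the last administration of study treatment must be reported to Novartis safety within 24 hours". Section 10.1.1 asks for AE monitoring for at least 30 days after the injection.

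On where later events are recorded, Table 8-1 marks AEs at Day 31 as source documentation only. Section 8.4 puts AEs after the End of Study visit in the source and sends SAEs to the sponsor's safety department. Section 10.1.3 adds: "Safety events occurring during the study will be reported as AEs in the eCRF".

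Protocol 12.4.2 defines treatment-emergent events without an end date. SAP Section 4 lists seven changes to the protocol's analyses (medical history, exposure, concomitant therapies, SMQ, fellow eye, IOP, vital signs). None concerns the end of the window.

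**The concern.** AE incidence is the only endpoint of this study. The sponsor will receive SAEs for 30 days after injection under its own rule, but the tables can count only those that start by about Day 8. A subject with a new SAE on Day 12 would be reported to safety and yet be absent from the SAE summary and from the public SAE table.

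Nothing in the plan requires the tables to state the cut-off in a title or footnote. A reader who knows the 30-day reporting rule could take the SAE percentage as covering all 30 days.

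The unwindowed listings in SAP 2.8.1 and 2.8.2 would show such an event only if it reaches the clinical database, and the documents do not assure that.

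**Working it through.** **Inputs**
- Day count: "The date of the injection of study treatment will be defined as Day 1" (SAP 2.1.1.1), so k days after injection is Day k + 1.
- Visit 2: 7 ± 2 days after injection (protocol 6.1.3).
- End of SAE reporting: 30 days after injection (protocol 10.1.3).
- Planned size: approximately 30 subjects (protocol 5).

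**The plan's own days.** Visit 2: 1 + 7 = Day 8. Thirty days after injection: 1 + 30 = Day 31. Both match the nominal days in Table 8-1. The visit window is Day 6 (1 + 5) to Day 10 (1 + 9).

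**Reportable days after the cut-off.** If the window closes at the end of Day d, the days not covered are 31 − d.

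| Case | d | 31 − d | Share of 30 days |
|---|---|---|---|
| Visit 2 late in window | 10 | 21 | 70% |
| Visit 2 nominal | 8 | 23 | 77% |
| Visit 2 early in window | 6 | 25 | 83% |
| Discontinued on Day 3 (example) | 3 | 28 | 93% |

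If the completion day itself is not counted, the range for subjects seen in the window becomes 22 to 26. A visit held after its window leaves fewer days uncovered.

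**Effect on a table.** One subject whose only SAE starts after Visit 2: 1/30 = 3.3 percentage points. If no other subject has an SAE, the table shows 0/30 instead of 1/30.

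**How likely is one such subject?** The documents give no SAE rate. As an illustration only, assume 30 subjects, a 30-day SAE risk p per subject, and onset spread evenly over the 30 days. The chance of at least one SAE in the e uncovered days is 1 − (1 − p·e/30)^30.

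| Assumed p | e = 21 | e = 23 | e = 25 |
|---|---|---|---|
| 1% | 19% | 21% | 22% |
| 2% | 35% | 37% | 40% |
| 5% | 66% | 69% | 72% |

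**Is there a data route?** Protocol 8.1.1 says of screen failures: "No further data will be entered into the clinical database for subjects who are screen failures, except if subject experienced a serious adverse event". No equivalent sentence covers treated subjects after Visit 2. The eCRF sentence in 10.1.3 applies during the study, and a subject's study ends at Visit 2. Section 10.1.1 asks in general for AEs to go on the AE CRF, but Table 8-1 and 8.4 point to the source documents for this period. Moving the SAP date alone may therefore not bring these SAEs into the tables; the SAP must also name the source.

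**When could the data be complete?** Protocol 4.2 and Table 8-1 place the follow-up call at Day 31. Section 8.4 places it 30 days after the End of Study visit, and only for subjects with ongoing AEs: Day 6 + 30 = 36 to Day 10 + 30 = 40. An SAE with onset by Day 31 that is first learned of at such a call would miss a lock set at Day 31.

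**The case against.** The strongest reply is that the limit starts in the protocol. If AEs after Visit 2 are recorded only in the source, the SAP closes its window where clinical-database collection closes and removes little that the tables would otherwise hold. A reporting period is also not an analysis period: SAE reporting starts at consent and treatment-emergent summaries start at injection, which nobody calls an error. Protocol 12.4.3 describes two visits over one week, and a Visit 2 cut-off fits that. Protocol 12.4.2 gives no end date, so the SAP had to choose one, and it states its choice openly. With 30 subjects and no comparator, individual listings carry much of the information.

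Much of this stands. A reader might infer that the SAP contradicts the protocol's definition, or that it alone drops these events. The documents do not support that: the SAP fills a gap, and the protocol's recording rules share the cause. For non-serious AEs the limit comes mainly from those rules. A reader might also infer that 77% of SAEs are lost. That figure is calendar time, and nothing in the documents says how many SAEs fall in it. The missing Section 4 entry is a secondary transparency point.

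What does not stand is the conclusion that nothing needs changing. The one-week visit schedule does not explain leaving out SAEs that the sponsor must already receive under 8.4 and 10.1.3. A listing is not an incidence, and incidence is the endpoint.

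**Conclusion.** The point holds in a limited form. For a subject seen within the visit window, an SAE that starts in the last 21 to 25 of the 30 reportable days cannot be counted in the SAE summary or the ClinicalTrials.gov SAE table. The same is true of the death summary if it follows the definition in SAP 2.8.1. The SAP cut-off and the protocol's data route produce this together.

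Whether any subject is affected is unknown, and the number may be zero. The effect of 3.3 points per affected subject assumes a full analysis set of 30. The documents do not show that any SAE has been or will be left out. They show that the plan could not count one in this period. The remedy is a cheap improvement worth making before database lock.

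**What to change.** 1. In SAP 2.8.1, 2.8.1.1 and 2.8.2, summarise SAEs and deaths with onset through 30 days after injection, in separate columns for onset through Visit 2 and after Visit 2. Define treatment-emergent death on that window.
2. Name the sponsor's safety reports, reconciled before lock, as the source for SAEs after Visit 2. If eCRF entry is preferred, first check that Table 8-1 and 8.4 allow it.
3. Lock only when the 30-day period has ended for the last subject, the last planned follow-up call has been made and the SAE reconciliation is done. Protocol 4.2 and Table 8-1 disagree with 8.4 on the call, so these passages must be reconciled first to set that date.
4. Title the all-AE tables and the non-serious ClinicalTrials.gov table *onset through Visit 2*. Footnote that later SAEs appear only in the SAE table, and that ascertainment after Visit 2 is partly passive.
5. Note the cut-off in SAP Section 4.
6. Do not extend the non-serious AE window unless protocol 4.2, 8.4, 10.1.1 and Table 8-1 are reconciled on who is contacted, when, and where the events are recorded.

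Cost: a SAP edit, one reconciliation step and a later lock. After the last in-window Visit 2, the wait is at least 21 to 25 days, or 30 days if a call falls as 8.4 describes. SAE counts after Visit 2 will be less complete than those before it, which is why they need their own column. The SAE table will also no longer be a subset of the all-AE table, which the footnote must make plain.
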